#### 9.5.1 Primary Outcome

• percentage of complete on-site data sets

#### 9.5.2 Secondary Outcomes

With regard to Phase I of the trial feasibility parameters will be

- number of enrolled patients by day 150 after initiation of recruitment in the clinic (=day 1)
- number of returned packages of filled out diary cards.
- percentage of patients in app group listen to app ≥5 min

With regard to Phase I

- anxiety on a validated 0-10 scale in the dental waiting room
- pain on a validated 0-10 scale in the dental waiting room
- anxiety q10 min (+/- 2 mins) on during dental treatment
- pain q10 min (+/- 2 mins) during dental treatment
- anxiety, average, and maximal anxiety for 7 days after treatment
- pain, average and maximal pain for 7 days after treatment
- use of prescription and nonprescription drugs for 7 days after treatment
- patient satisfaction

•

Pain and anxiety will be measured on 0-10 verbal self-reporting scales (0=no pain/anxiety at all, and 10=worst pain possible). The pain scale is recommended standard in the NIH Toolbox (62). For the 0-10 anxiety scale we previously demonstrated convergent and discriminant validity (63).

Anxiety and pain measures will obtained using these scales by verbally asking the patient "How is your Comfort Level on a scale with 0-no anxiety at all, and 10 worst anxiety possible and 0=no pain at all and 10=worst pain possible":

- At the beginning of the waiting room time after consent
- At the end of the waiting room time
- After the patient enters the dental treatment room and sits down = time 0 of chair time
- Every 10 minutes (+/- 2 minutes) thereafter while on the chair
- When leaving the dental treatment room

Once returned home the patients are asked to use the same scales to write down on daily diary cards for 7 days before bedtime as follows:

PLEASE INDICATE YOUR COMFORT LEVELS WITH A NUMBER BETWEEN 0 and 10

With regard to pain (0=no pain at all and 10=worst pain possible)

- Right now:
- On the average today:
- At its maximum today:

With regard to anxiety (0=no anxiety at all and 10=worst anxiety possible)

- Right now:
- On the average today:
- At its maximum today:

Patient Satisfaction will be assessed using a modified Press Ganey Outpatient Survey template (64) adjusted to dental care and supplemented with a question regarding helpfulness of the app on the same 5-point scale as the remainder of the survey. The Press Ganey instrument has been found to possess suitable psychometric properties for outpatient medical practice survey (65).

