### Phase II preparation

primary outcome parameter

• anxiety at the end of the waiting room time

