#### **Baseline Assessments**

Once the patient is enrolled *Demographics* and *History* will be recorded on the Tufts University School of Dental Medicine Research Participant& Dental History form (Appendix).

Assessments include:

- Age
- Gender
- Race
- Medical history
- Medications

*Eligibility and withdrawal criteria* will be rechecked prior to randomization by going through the CRF form.

The participant will be asked to complete a *NIDA Quick Screen*. No identifiable information will be collected on the NIDA Quick Screen (only the subject ID number). The NIDA (National Institute on Drug Abuse) Quick Screen will be used to assess drug use (including tobacco, alcohol and illegal substances) and nonmedical use of prescription drugs. The NIDA Quick Screen is a brief questionnaire that addresses overall substance use risk, with likely utility for use in a dental setting. This screening tool is intended to be used by doctors serving adult patients in general medical settings. Its algorithm also identifies patients in need of counseling. The instrument is not used as legal-criminal screen. Furthermore, the NIDA is expected to be a routine tool for the history intake at the Craniofacial Pain Center as an important clinical tool in patient assessment.

The information collected via the NIDA quick screen will be compared to post-visit self-reported medication data from the diary, in order to evaluate any changes in opioid use after their dental visits

The participant will then be verbally asked to indicate his/her *anxiety and pain levels* on validated 0-10 scales (0-no pain/anxiety at all, 10-worst pain/anxiety possible). The research assistant will ask about their pain and anxiety using the same verbiage provided on the patient diary, and record their response.

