## 9.2 Sample Size and Randomization

The goal is to enroll 72 patients in a randomized design with 36 patients utilizing the app and 36 patients not utilizing the app. Those randomized to utilizing the app (app group) will receive a tablet with the app, those randomized to not utilizing the app (control group) will receive a tablet with white noise.

Based on prior trial experience, it is likely that 90% of patients on site will provide onsite data sets (primary objective). In two prior trials, in which 241 and 201 patients, respectively, were followed through their invasive medical procedures, all enrolled patients (100%) provided these data (1,3). In a breast-biopsy trial, 4 of 240 (1.6%) withdrew by that stage (2). In these past trials patients received more personal attention through live delivery of the content that is now offered in an app, and thus willingness to remain in the study may not be as high in the current trial but still should exceed 90% for feasibility. To arrive at a reasonable sample size to satisfy this requirement, but also obtain a sense of validity of the primary hypothesis for Phase II and obtain estimates of data distribution, which will be critical for sample size and analysis planning Phase II, we conducted following sample size calculations.

Assuming an average anxiety rating of 4 at the end of the waiting room time without prior guidance in relaxation or app (see Fig 3., time 0), the expectation of improved subsequent outcomes with a 35% reduction in anxiety to 2.6 based on Schupp et al (33 vs 53 on STAI - (1) and a standard deviation of 2, 66 patients would be needed for a two-sided test with a power of 0.80 and an alpha of 0.05.

This degree of reduction in anxiety is clinically significant based on prior work in a clinical trial that demonstrated that a 35% difference in anxiety at the onset of an invasive medical procedure is associated with significant differences in the subsequent experience of pain and anxiety during the procedure, need for opioid analgesics and sedatives, and the overall length of the procedure. These factors directly affect procedure safety and throughput (e.g. economical efficiency).

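### The anxiety rating is asked as a comfort level on a scale where 10 is worst, so reversed answers are possible; if they occur, they could cost power and distort Phase II sizing

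*Combined protocol and SAP*

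**What the plan says.** Section 9.5.2 defines pain and anxiety as 0-10 verbal ratings on which 0 is none and 10 is worst. It then scripts the spoken question as "How is your Comfort Level on a scale with 0-no anxiety at all, and 10 worst anxiety possible", and the same sentence goes on to give the pain anchors. The question is put at the start and end of the waiting room time, on sitting down in the dental chair, about every 10 minutes after that, and on leaving the treatment room.

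The take-home diary carries the heading "PLEASE INDICATE YOUR COMFORT LEVELS WITH A NUMBER BETWEEN 0 and 10". Below it are separate blocks for pain and for anxiety, each with its own anchors. Section 6.2.2 (Baseline Assessments) ties the baseline question to the diary: "The research assistant will ask about their pain and anxiety using the same verbiage provided on the patient diary".

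The Précis (Phase II preparation) and section 3 name "anxiety at the end of the waiting room time" as the Phase II primary outcome. In this pilot it is a secondary clinical outcome; the pilot's primary outcome (9.5.1) is the "percentage of complete on-site data sets". Section 9.6 bases the Phase II sample size on Phase I results, and proposes to compare the change from start to end of the waiting room time by t-test, or by Mann-Whitney if the data are not normal.

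**The concern.** The stem and the anchors run in opposite directions. A patient asked for a comfort level who feels very comfortable may well say 9 or 10, but the form needs 0 or 1. Asking for two numbers in one spoken sentence adds to the chance of a slip.

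Reversals at the same rate in both arms pull the observed difference toward zero and widen the spread. Two things are then at stake: power for the anxiety comparison in this pilot, and the difference and SD passed on to Phase II planning. The documents describe no check for reversed answers. Section 9.5 treats the ratings as plain numbers that need no interpretation.

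**Working it through.** **Inputs.** From section 9.2: control mean 4 ("Assuming an average anxiety rating of 4 at the end of the waiting room time"), app mean 2.6 ("35% reduction in anxiety to 2.6"), SD 2 and total 66 ("and a standard deviation of 2, 66 patients would be needed"), two-sided alpha 0.05, power 0.80, 72 enrolled at 36 per arm, and 6 drop-outs expected, leaving 66 (33 per arm). The reversal rate *r* is not in the documents; the values below are assumptions.

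**The plan's own figure.** n per arm = 2(1.960 + 0.842)² × 2² / 1.4² = 32.04, rounded up to 33, so 66 in total. This matches the plan. Power by the normal approximation is 81% with 33 per arm and 84% with 36.

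**End score with reversals.** Suppose a share *r* in each arm answers 10 − x instead of x. Then:
- difference = 1.4(1 − 2r)
- variance in an arm with mean m = 4 + r(1 − r)(10 − 2m)², with the two arms averaged
- power = Φ(difference / (SD × √(2/n)) − 1.96)

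At r = 0.05:
- The difference is 1.4 × 0.90 = 1.26.
- The control variance is 4 + 0.0475 × 2² = 4.19.
- The app variance is 4 + 0.0475 × 4.8² = 5.09.
- The averaged SD is √4.64 = 2.15.
- With 36 per arm, 1.26 / (2.155 × 0.2357) − 1.96 = 0.52, which gives power 70%.

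| Reversed (assumed) | Difference | SD | Power, 33 per arm | Power, 36 per arm | Total N for 80% |
|---|---|---|---|---|---|
| 0% | 1.40 | 2.00 | 81% | 84% | 66 |
| 2% | 1.34 | 2.07 | 75% | 79% | 76 |
| 5% | 1.26 | 2.15 | 66% | 70% | 92 |
| 10% | 1.12 | 2.28 | 51% | 55% | 132 |

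Simulated t-tests on whole-number scores held to 0-10, with 33 per arm, give 78%, 63% and 49% at 0%, 5% and 10%. The pattern is the same, at a slightly lower level.

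**Planned change score.** Section 9.6 compares change, so the end-score figures are not the planned analysis. Assume a start-to-end correlation of 0.5, a mean of 4 at the start in both arms, no mean change in controls, and the same patients reversing both times. Reversal then flips the sign of the change:
- The SD of change is 2√(2 × 0.5) = 2.
- The difference is again 1.4(1 − 2r).
- The app-arm variance is 4 + 4r(1 − r) × 1.4²; the control variance stays 4.

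At r = 0.05 the app variance is 4.37, the averaged SD is 2.05 and the difference is 1.26. With 33 per arm, power falls from 81% to 71%. At 10% it is 59%.

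**The case against.** The best defence is that the anchors are spoken inside the question, by a research assistant who is face to face with the patient and asks it repeatedly. The diary prints separate pain and anxiety blocks with their own anchors. Section 9.6 also plans graphs of each patient's ratings, which could show up an answer in the wrong direction. No passage reports a reversed answer or a comprehension problem. All of this stands. It makes high reversal rates less likely and rules out saying that power *is* lost. It does not remove the mismatch in the stem, and even an assumed 2% costs about 5 or 6 points of end-score power.

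Section 9.5.2 also cites earlier validation of the 0-10 anxiety scale. The documents do not say whether that version used the comfort stem. If it did, rewording would give up some comparability; if it did not, rewording would bring the question closer to the validated form. The documents cannot settle this.

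A reader might also infer that the stem primes the app arm, because the product is called Comfort Talk and one of its menu topics is Comfort. The documents do not support that. By 9.5.2 and 6.2.2, both arms meet the comfort wording at baseline, before any tablet is handed over. Comfort is one of four topics that a patient may choose, and listening is optional (section 2.2, Administration of Intervention). Neither a direction nor a size for such an effect can be derived.

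**Conclusion.** The wording is a real but minor weakness, and correcting it is a cheap, optional improvement. The mismatch between stem and anchors is plain in the text; the loss is conditional. If 2% to 10% of answers were reversed at equal rates in both arms, end-score power with 36 per arm would drop from about 84% to between 79% and 55%. The planned change score, under the assumptions given, loses about 10 points at 5%. At that rate Phase I would also pass on a difference of 1.26 instead of 1.40 and an SD of 2.15 instead of 2.00. Sizing on those values would call for 92 patients rather than 66.

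Two stronger readings should be resisted. The sample size of 66 is not in error, since it reproduces from its stated inputs. Nor is the pilot's feasibility verdict at risk, because completeness of on-site data does not depend on the direction of an answer.

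**What to change.** In the spoken script and on the CRF, ask two separate questions that name what is rated and keep the existing anchors. For example: *How is your anxiety right now, from 0 for none to 10 for the worst possible?*, followed by the same for pain. On the diary, replace the comfort wording in the heading with words that name pain and anxiety; the separate blocks below can stay. Use the same spoken wording at baseline and at every later on-site time, so that 6.2.2 and 9.5.2 agree.

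The change needs no extra patients, visits or analyses, and it leaves the sample-size figures as they are. The cost is a revision of the script, CRF and diary, and a wording difference from any earlier forms that used the comfort stem.

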#### 6.2.5 Completion/Final Evaluation

The outpatient visit at the time of enrollment is the participant's first and at the same time final visit with regard to the study.

After obtaining the baseline data the research assistant will hand the participant a tablet containing, depending on the group attribution, either the app (App Group) or white noise (Control Group) and will be shown how to operate the tablet.

Participant will then return to the clinic waiting area with the tablet and wait for their regularly scheduled appointment. The patient will be at liberty to when and for how long to listen.

At the end of the waiting room period the participant will be queried again for their levels of pain and anxiety.

After the participant enters the treatment room, he or she will be able to continue to listen to the app or white noise on the tablet. The treating dental practitioner will not be made aware of the group attribution and conduct the treatment as usual. The research assistant will ask the participant every  $10 \min{(+/-2 \text{ minutes})}$  to indicate their pain and anxiety levels. The research assistant will note the duration of chair time, the amount of lidocaine given, if any or which other medications were given during the appointment, and whether the dental practitioner prescribed opioid, prescription or non-prescription drugs at the end of the visit. This information will be obtained by the research assistant from the standard of care provider at the end of treatment.

Before leaving home, the participant will be asked to fill out a satisfaction survey based on a modified Press Ganey Template. The participant will then receive a diary card on which to note pain, average and maximal pain as well its location, use of non-prescription, prescription, and opiate drugs, use of the app, and be provided prestamped envelopes. Patients will be asked to complete the diary daily before bedtime for 7 days. Patients in the experimental group will receive a coupon (coded by group) for free download of the app at the end of their study visit.

Once the diary is mailed back and received by the study team, the participant will be sent a check in the mail. Participants randomized to the control condition will also receive a coupon for the app upon returning the diary.

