#### 9. STATISTICAL CONSIDERATIONS

## 9.1 General Design Issues

This randomized controlled trial is a single-site pilot trial to assist in feasibility assessment and sample size estimation in a pivotal trial to test the hypothesis that listening to a Comfort Talk® app with calmative content reduces pain, anxiety, and post-procedural medication use. The study design is based on a 1:1 randomized attribution of participants to an app or white noise as control condition.

The feasibility criteria are not hypothesis driven and are based on practical pass/fail criteria:

primary feasibility outcome parameter:

• ability to obtain complete on-site data sets from at least 90% of patients enrolled - with at least 40% from patients in the app group and at least 40% from patients in the control group)

secondary feasibility outcome parameters:

- ability to enroll 60 patients by day 150 after initiation of recruitment in the clinic (=day 1)
- obtaining 38 packages of filled out diary cards (at least 16 from patients in the app group and at least 16 from patients in the control group).
- 90% of patients in app group listen to app  $\geq$ 5 min

Since a significant reduction in anxiety in the waiting room is the main ingredient that underlies all other hypothesized effects for Phase II outcomes, even in the face of proven technical feasibility of trial execution, it was chosen as the overall primary objective for Phase II.

Statistical hypotheses for Phase II are:

Providing participants a calmative Comfort Talk® app at the time of their dental outpatient visit

- reduces anxiety in the dental waiting room (primary hypothesis)
- reduces pain in the dental waiting room
- reduces anxiety during dental treatment
- reduces pain during dental treatment
- improves patient satisfaction with the dental visit
- reduces anxiety in the week after treatment
- reduces pain in the week after treatment
- reduces need for opioids and analgesics the week after treatment

The overall premise is that showing patients at the time they experience distress how to cope while they are still under physician/dentist supervision will carry over into recovery and thus reduce need for addictive drugs (see also 2.2).

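### The first diary card is undated and asks about the whole day, so its average and maximum ratings can include the visit that the week-after outcomes are meant to follow

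*Combined protocol and SAP*

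**What the plan says.** Section 9.5.2 names as outcomes "pain, average and maximal pain for 7 days after treatment", "anxiety, average, and maximal anxiety for 7 days after treatment" and "use of prescription and nonprescription drugs for 7 days after treatment". The instruction there is "Once returned home the patients are asked to use the same scales to write down on daily diary cards for 7 days before bedtime". Section 6.2.5 has the participant receive the diary before leaving the clinic and adds "Patients will be asked to complete the diary daily before bedtime for 7 days". Each card asks for three ratings of pain and three of anxiety: the level at the moment of completion, "On the average today" and "At its maximum today".

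Section 9.5.2 also lists anxiety and pain in the waiting room and in the dental chair as outcomes of their own, the chair ratings being taken every 10 minutes. The précis (Design and Outcomes) describes the diary as covering seven days following the visit.

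No section dates card 1, and none limits a visit-day rating to the hours after departure. Section 9.6 compares per-patient slopes and per-patient means over the diary week. It does not name which of the three ratings is used and has no rule for a card completed on the day of the visit. Section 9.1 states the premise under test, that coping shown in the clinic "will carry over into recovery and thus reduce need for addictive drugs".

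**The concern.** A patient who leaves with the cards and is told to fill one in at bedtime once home will most naturally start that evening. On that card the day's average and maximum cover the hours before arrival, the waiting room, the chair and the hours afterwards. The worst moment of the day may well be the procedure.

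An effect that exists only in the clinic would then appear in outcomes labelled as following treatment, even if nothing carries over. It would also be counted twice, because the waiting-room and chair ratings already measure it. Patients who start the next evening report a different period on the same card, so card 1 is not one measure across patients. Section 9.6 bases the Phase II sample size on the Phase I results, so the pilot is the right time to settle what the instrument measures.

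For drug use the point is narrower. The document does not show the wording of the drug item, so all that can be said is that no section limits card-1 drug use to the time after departure.

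**Working it through.** **Inputs from the plan.** Waiting-room anxiety of 4 against 2.6, SD 2 (Section 9.2). Day-1 pain of 3.5 against 1.6, SD 2.0, 38 patients in total (Section 9.2). Seven cards (Section 9.5.2). A visit of about 1.25 hours (précis, Interventions and Duration).

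**Assumptions not in the plan.** The arm difference exists only in the clinic; a share k of it reaches the card-1 maximum; a waking day lasts 14 to 18 hours.

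**1. The plan's own diary figure.** The difference is 3.5 − 1.6 = 1.9. The normal approximation gives 2 × (1.96 + 0.84)² × 2.0² / 1.9² = 17.4, so 18 per arm and 36 in total. The two-sample t-test gives 19 per arm and 38 in total. The stated 38 is reproduced and is not in dispute. The text does use day 1 without saying which diary card that is.

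**2. What card 1 covers.**

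| Start of diary | Hours inside the card-1 average and maximum |
|---|---|
| Visit evening | before arrival, waiting room, chair, after departure |
| Next evening | after the visit only |

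Sections 9.5.2 and 6.2.5 point to the first row. The précis fits either.

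**3. Weight of card 1 in the Section 9.6 summaries.** In a 7-card mean it is 1/7 = 0.143. In a least-squares slope over days 1 to 7 the mean day is 4 and the sum of squares is 9 + 4 + 1 + 0 + 1 + 4 + 9 = 28, so the weight is (1 − 4)/28 = −3/28 = −0.107.

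**4. Upper bound for the maximum item (k = 1).** Take 4 − 2.6 = 1.4 points, the waiting-room anxiety difference hypothesised in Section 9.2, as a gap confined to the clinic and fully reflected in every patient's card-1 maximum.
- Mean, app minus control: −1.4 / 7 = −0.20 points, which favours the app.
- Slope, app minus control: −1.4 × (−3/28) = +0.15 points per day. A lower first card makes the app arm's decline look flatter, which counts against the app.

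**5. Range over k.** Both figures scale with k.

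| k | Shift in mean of daily maxima | Shift in slope, per day |
|---|---|---|
| 0.25 | −0.05 | +0.04 |
| 0.50 | −0.10 | +0.075 |
| 1.00 | −0.20 | +0.15 |

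**6. The daily-average item.** If the average is weighted by time over 16 waking hours, the visit is 1.25/16 = 7.8% of the day. Card 1 then shows 1.4 × 0.078 = 0.11 points, and the 7-card mean 0.11/7 = 0.016. With 14 to 18 waking hours the mean shifts by 0.018 to 0.014.

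**The case against.** The strongest reply is that no section assigns card 1 to the visit day. The outcome labels and the précis both fit a next-day start, and under that start the overlap disappears. This stands to the extent that the overlap cannot be stated as fact. It does not dispose of the point, because nothing requires a next-day start either, and an undated card lets patients choose.

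Several further objections are sound and limit the finding:
- The momentary ratings are untouched, and Section 9.6 may intend to analyse those. However, Section 9.5.2 names average and maximum as outcomes.
- The 1.4 points is a waiting-room anxiety hypothesis, not an estimate of a difference in daily maxima or in pain. Many of the procedures are appliance fittings and adjustments in a pain clinic, so the day's peak may often fall elsewhere.
- Hours before arrival fall on both randomised arms alike. In expectation they add noise or dilute a difference; they do not favour an arm. Only the clinic hours after the tablet is handed over can carry an arm difference.
- App patients may use the app at home during the week, so the comparison never isolated carry-over from the clinic. That is a separate limitation. Both carry-over and home use are effects after departure, and ratings of the procedure itself are neither.
- Section 9.6 calls the clinical analyses provisional and promises descriptive statistics by time point, so card 1 can be inspected on its own. Inspection cannot show which hours a patient had in mind.

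A reader might infer that analgesics or sedatives taken before the visit will be counted as use after treatment. The documents do not support this, because the recall wording of the drug item is not shown and the diary form is only listed as an appendix.

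**Conclusion.** The point holds in a limited form. The start of the diary week and the period covered by card 1 are not fixed. Followed as written, the most natural reading brings in-clinic experience into the average and maximum ratings that are labelled as post-treatment outcomes. A mixture of start days would make card 1 differ in meaning between patients.

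The size is modest. The upper bound for the maximum item is 0.20 points in the weekly mean, one tenth of the plan's SD of 2 for a single rating, and 0.15 points per day in the slope. It rests on a 1.4-point gap confined to the clinic and reaching every patient's card-1 maximum. The two shifts have opposite signs, so the two planned summaries could disagree through the recall window alone. For the daily average the shift in the mean is about 0.02 points.

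Two stronger inferences should be resisted. One is that the week-after outcomes are certainly contaminated, which would need a dated card 1. The other is that the 38-patient figure is wrong: it reproduces, and the documents give no basis for saying how much of card 1 precedes the intervention. The primary feasibility outcome and the diary-return count are not affected. This is a cheap improvement to secondary outcomes, not a threat to the pilot's main purpose.

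**What to change.** Pre-date the cards so that every patient starts on the same day relative to the visit. If card 1 is the visit evening, replace *today* on that card with *since you left the clinic* for average, maximum and drug use, and leave cards 2 to 7 as they are. State in Section 9.5.2 that the week-after outcomes begin at clinic departure. It would also help to name in Section 9.6 which rating enters the means and slopes.

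The cost is one reprinted card, a sentence in 9.5.2 and IRB notification; Section 11.1 also routes modifications through NCCIH. The drawback of a visit-evening card 1 is a shorter window than on the other cards, and one that varies with appointment time. A uniform next-day start avoids that but loses the first evening.
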